pSS Table 8 lists the complete sampling schedule for assessment of the PK of branebrutinib, metabolites, and concomitant medications in subjects with pSS.

To assess steady-state concentrations of branebrutinib, a total of 5 predose PK samples (approximately 4 mL each) will be drawn from all study subjects at Week 0 (Day 1), Week 4 (Day 29), Week 8 (Day 57), Week 16 (Day 113), and Week 24 (Day 169). (Note that these samples will be drawn within a 1-hour window before the next dose is administered.) For subjects at preselected sites with extended sampling, predose PK samples collected at Week 8 (Day 57) will also be aliquoted to assess metabolite concentrations.

For postdose sampling, all study subjects will have branebrutinib PK samples drawn at Week 0 (Day 1), Week 8 (Day 57), and Week 24 (Day 169) at the 0.5, 1, 2, and 4-hour time points, a total of 14 samples. (Note that these samples will be drawn within ± 15 min from the given time points.) For subjects at preselected sites with extended sampling, postdose PK samples will be aliquoted to assess metabolite concentrations at these time points.

Protocol Amendment No.: 04

In addition, for subjects at preselected sites with extended sampling, a total of 7 postdose PK samples will be drawn and assessed for both branebrutinib and metabolite concentrations at Week 0 (Day 1) and Week 8 (Day 57) at approximately 06:00 hours, and from 08:00 to 10:00 hours (flexible window), and from 10:00 to 12:00 hours (flexible window). Samples will also be collected at Week 0 (Day 2) at approximately 24:00 hours postdose (predose of branebrutinib on Day 2). Efforts should be made to collect the samples within these windows; however, any sample drawn outside the prespecified window will not be considered a protocol deviation. Both planned and actual time points at which the blood samples will be taken will be recorded and used in analysis and modeling.

Concomitant Medications

Concentrations of concomitant medications that are sensitive substrates of CYP2C8 and other potentially relevant drug metabolizing enzymes that may have a drug-drug interaction with branebrutinib and P-gp transporter may be measured (post-hoc) in subjects receiving PBO and active treatment. Samples for the PK assessment of the relevant concomitant medications will be collected at Week 0 and Week 4 from all study subjects. Samples for PK analysis collected from subjects receiving branebrutinib or PBO will be analyzed for HCQ and other relevant concomitant comedications provided that these subjects are receiving HCQ and other relevant concomitant comedications.

Detailed instructions for the collection, labeling, processing, storage, shipping, and disposition of all PK blood samples are provided in the Laboratory Manual.

pSS Table 8 PK Sampling for Branebrutinib, Metabolites, and Concomitant Medications

	Study Week		Time (Relative to Branebrutinib Dose) Hours:Minutes		Metabolites (collected from subjects at preselected sites)	Concom	Comments
1	0	Predose	00:00	X		X ^{a,b,c}	 Predose PK samples will be collected from all study subjects to assess branebrutinib and relevant concomitant medications; For subjects on HCQ, whole blood samples will be collected for HCQ level assessment.
1	0	Postdose	00:30	X	X		 Postdose PK samples collected from all study subjects at these time points will be assessed for branebrutinib; Postdose PK samples collected at these time points from subjects at preselected clinical sites will also be assessed for metabolites; Postdose PK samples collected at 2 hours after dosing, will be assessed for relevant
1	0	Postdose	01:00	X	X		
1	0	Postdose	02:00	X	X	x ^{a,b,c}	
1	0	Postdose	04:00	X	X		

Protocol Amendment No.: 04

pSS Table 8 PK Sampling for Branebrutinib, Metabolites, and Concomitant Medications

	Study Week	Event	Time (Relative to Branebrutinib Dose) Hours:Minutes	Branebrutinib	Metabolites (collected from subjects at preselected sites)	Concom	Comments	
							concomitant medications; • For subjects on HCQ, whole blood samples will be collected for HCQ level assessment.	
1	0	Postdose	06:00	X	X		• Postdose PK samples collected	
1	0	Postdose	08:00-10:00	X	X		from subjects at preselected clinical sites only will be	
1	0	Postdose	10:00-12:00	X	X		assessed for branebrutinib and	
2	0	Postdose ^d	24:00	X	X		metabolites at these time points.	
29	4	Predose	00:00	X		X ^{a,b,c}	 Predose PK samples will be collected from all study subjects for assessment of branebrutinib and concomitant medications; For subjects on HCQ, whole blood samples will be collected for HCQ level assessment. 	
29	4	Postdose	02:00			X ^{a,b,c}	 Plasma samples will be collected from all study subjects at 2 hours after dosing for assessment of relevant concomitant medications; For subjects on HCQ, whole blood samples will be collected in addition for HCQ level assessment. 	
57	8	Predose	00:00	X	X		• Predose and postdose PK	
57	8	Postdose	00:30	X	X		samples collected at these time	
57	8	Postdose	01:00	X	X		points from all study subjects will be assessed for branebrutinib	
57	8	Postdose	02:00	X	X		only.	
57	8	Postdose	04:00	X	X		• Predose and postdose P samples collected at these timpoints from subjects preselected clinical sites will also be assessed for metabolites.	
57	8	Postdose	06:00	X	X		• Postdose PK samples collected	
57	8	Postdose	08:00-10:00	X	X		at preselected clinical sites only	
57	8	Postdose	10:00-12:00	X	X		will be assessed at these time points for branebrutinib and metabolites.	
113	16	Predose	00:00	X			• Predose PK samples taken from all study subjects will be assessed for branebrutinib only.	

Clinical Protocol BMS-986195

pSS Table 8 PK Sampling for Branebrutinib, Metabolites, and Concomitant Medications

	Study Week		Time (Relative to Branebrutinib Dose) Hours:Minutes	Branebrutinib	Metabolites (collected from subjects at preselected sites)	Concom Meds ^{a,b,c}	Comments	
169	24	Predose	00:00	X			• Predose PK samples taken from all study subjects will be assessed for branebrutinib only.	
169	24	Postdose	00:30	X			• Postdose PK Samples taken at	
169	24	Postdose	01:00	X			these time points from all study subjects will be assessed for branebrutinib only.	
169	24	Postdose	02:00	X				
169	24	Postdose	04:00	X				

NA = not applicable; PK = pharmacokinetic; Concom Meds = concomitant medications; HCQ = hydroxychloroquine.

pSS 8.5.1 PK of Potential Concomitant Medications

Concentrations of Concomitant medications that are sensitive substrates of CYP2C8 and other potentially relevant drug metabolizing enzymes and P-gp transporter may be evaluated for subjects receiving PBO and active treatment with the bioanalytical analysis as part of a retrospective analysis. HCQ will be among the concomitant medications. The retrospective analysis will be conducted after review of the enrollment records, reported concomitant medication use within the enrolled population and on the incidence threshold and relevance to drug interaction with branebrutinib based on preclinical and clinical data. Other confounding factors will be evaluated as part of the analysis to avoid inclusion of bias or artifact results.

Subjects who are on HCQ will be informed to bring HCQ to the clinic on Day 1 and Day 29 for simultaneous dosing with branebrutinib and not to take it at home on those 2 days. Similarly, subjects who are on other prescription concomitant medications will also be informed to bring them to the clinic on Day 1 and Day 29 for simultaneous dosing with branebrutinib, but only when it is safe for subjects and operationally feasible. This should be based on the investigator's

a Concentrations of concomitant medications that are sensitive substrates of CYP2C8 and other potentially relevant drug metabolizing enzymes that may have a drug-drug interaction with branebrutinib and P-gp transporter may be evaluated post-hoc for subjects receiving PBO and active treatment at predose of branebrutinib on Day 1 and Day 29 (see Section pSS 8.5.1).

b For subjects taking HCQ on-study, whole blood samples will be taken at predose and 2 hours after dosing with the IP on Day 1 (Week 0) and Day 29 (Week 4) (see Section pSS 8.5.1).

Subjects who are on HCQ will be informed to bring HCQ to the clinic on Day 1 and Day 29 for simultaneous dosing with branebrutinib and not to take it at home on those 2 days. Similarly, subjects who are on other prescription concomitant medications will also be informed to bring them to the clinic on Day 1 and Day 29 for simultaneous dosing with branebrutinib, but only when it is safe for subjects and operationally feasible. This should be based on the investigator's discretion with consideration that the medications which should not be delayed until the time of dosing in the clinic should be taken at home. The self-reported time for all prescription medications taken at home should be recorded as accurately as possible.

d PK sample must be drawn before the IP dose is administered on Day 2.

discretion with consideration that the medications which should not be delayed until the time of dosing in the clinic should be taken at home. The self-reported time for all prescription medications taken at home should be recorded as accurately as possible.

The concentrations of relevant concomitant medications will be measured, post-hoc, using samples collected predose of branebrutinib or placebo on both Day 1 and Day 29 (Week 4; at which point accumulation of branebrutinib and its metabolites is expected to achieve steady-state). In addition to predose samples on Day 1 and Day 29, samples will also be collected at 2 hours after dosing with branebrutinib or placebo to evaluate the concentration of relevant concomitant medications, including HCQ. Bioanalytical analysis of all relevant concomitant medications will be conducted post-hoc. The doses of the concomitant drugs and the time they are taken, will be carefully recorded at all times (including Day 1 on Week 0 and on Day 29 on Week 4). Actual and dose-normalized concentrations will be listed, summarized, and compared between posttreatment and pretreatment of branebrutinib and PBO separately; other covariates such as MTX use, gender, etc. can be added to the comparison as needed.

[figure not shown]
Detailed instructions for PK sample collection for the relevant concomitant medications, labeling, processing, storage, shipping, and disposition are provided in the Laboratory Manual. While blood samples will be used for the analysis of HCQ, plasma samples will be analyzed for the other relevant concomitant medications by available validated assays. The results of these post hoc analyses will not be recorded in the CSR.

Protocol Amendment No.: 04

[figure not shown]

Clinical Protocol BMS-986195

pSS 8.7 Health Economics OR Medical Resource Utilization and Health Economics

Health Economics/Medical Resource Utilization and Health Economics parameters will not be evaluated in this study.

PSS 9 STATISTICAL CONSIDERATIONS

pSS 9.1 Sample Size Determination

Sample size is calculated based on the estimated effect size for the primary endpoint comparison between branebrutinib and PBO treatment groups. The primary endpoint for the pSS sub-protocol is pSS composite response at Week 24.

Estimates for response rates were obtained from the published literature.^{82, 83} Sample size justification is provided below:

Assuming a total sample size of 45 subjects randomized in a blinded fashion at a 2:1 ratio to branebrutinib (30 subjects) or PBO (15 subjects) and a treatment difference of 30% with a PBO response of 20% for the pSS composite response at Week 24, the 95% CI is expected to exclude 0 (expected 95% CI based on a z-test = 3%, 57%).

pSS 9.2 Populations for Analyses

The following analysis sets will be used in the summary and analysis of study data:

Population	Description
Enrolled Set	All subjects who sign informed consent.
	All subjects who are randomized. Following the intent-to-treat principle,
FAS	subjects will be analyzed according to the treatment assigned at
TAS	randomization. The FAS will be the primary efficacy analysis population.
	This is the same as the intent-to-treat population.
	A subset of the FAS who are compliant with study treatment and who do
	not have any statistically relevant protocol deviations that may impact the
PPS	primary efficacy endpoint assessments. The PPS will be analyzed according
	to the treatment assigned at randomization. The PPS will be a supportive
	efficacy analysis population.
	All randomized subjects who receive at least 1 dose of double-blind study
	treatment. Subjects will be analyzed according to treatment received. In
	case subjects take the incorrect treatment, the following scenario will be
	considered:
	• For subjects who should be receiving branebrutinib treatment, if the
Safety Analysis	subject took any placebo dose, the subject will still be counted in
Set	branebrutinib treatment group for safety analysis set unless the subject
	took placebo throughout the entire course.
	For subjects who should be receiving placebo treatment, if the subject took
	any branebrutinib dose, the subject will be counted in the branebrutinib
	treatment group for safety analysis set.
	1

Protocol Amendment No.: 04

Population	Description
	All randomized subjects who receive at least 1 dose of branebrutinib and
PK	have any available branebrutinib concentration data. Subjects will be
	analyzed according to treatment received during the PK collection.
Biomarker	All randomized subjects who receive at least 1 dose of double-blinded study
Diomarker	treatment and have at least 1 posttreatment biomarker measurement.

pSS 9.3 Endpoints

The following sections outline the efficacy endpoints for this study.

pSS 9.3.1 Primary Endpoint

Proportion of subjects with at least 3 of the following at Week 24:

- Decrease of ≥ 1 point or 15% from baseline in the ESSPRI Total Score
- Decrease of \geq 3 points from baseline in ESSDAI score
- Decrease of \geq 25% from baseline in ocular staining score or, if normal score at baseline no change to abnormal
- Increase of $\geq 25\%$ from baseline in stimulated salivary flow
- Improvement in one or more serological markers (RF, IgG, complement C3 or C4, cryoglobulin)

pSS 9.3.2 Additional Endpoints

The following are the additional efficacy endpoints as defined at Week 24:

Proportion of subjects with the following at Week 24:

- Decrease of \geq 1 point or 15% in the ESSPRI Total Score
- Decrease of \geq 3 points from baseline in ESSDAI score
- Decrease of $\geq 25\%$ from baseline in ocular staining score or, if normal score at baseline no change to abnormal
- Increase of \geq 25% from baseline in Schirmer's test score or, if normal score at baseline no change to abnormal
- Increase of ≥ 25% from baseline in TBUT or, if normal score at baseline no change to abnormal
- Increase of $\geq 25\%$ from baseline in stimulated salivary flow
- Improvement in one or more serological markers (RF, IgG, complement C3 or C4, cryoglobulin)

Change from baseline in:

[figure not shown]
• Autoantibody titers, hsCRP, and ESR at Week 24

Clinical Protocol IM014029 - pSS BMS-986195 Branebrutinib

- DAS28-CRP
- EQ-5 D-5 L scores at Week 24
- PROMIS Fatigue 6 a
- PGA and SGA
- NRS for Mouth and Eye Dryness

pSS 9.3.3 PK Endpoints

• Concentration values and PK parameters of branebrutinib and metabolites of clinical interest

Protocol Amendment No.: 04

pSS 9.4 Statistical Analyses

The SAP will be developed and finalized before database lock. Section pSS 9.4.1 provides a summary of planned statistical analyses of the primary and secondary efficacy endpoints. Additional and exploratory endpoints will be summarized in a descriptive manner.

pSS 9.4.1 Efficacy Analyses

Efficacy data will be summarized using the FAS. Data will be summarized using descriptive statistics (n, mean, standard deviation, median, minimum, and maximum), unless otherwise specified, for continuous variables and frequency distributions (counts and percentages) for categorical variables. Efficacy data will be summarized separately for each sub-protocol and with each sub-protocol combined for variables that are similar among the sub-protocols.

For the pSS sub-protocol, data will be presented for the following treatments:

- Branebrutinib
- PBO

Endpoint	Statistical Analysis Methods		
	General Analysis Methodology		
	Response rates of branebrutinib compared to PBO for binary endpoints		
	(responder/nonresponder) will be analyzed using a CMH test stratified by HCQ		
	use. The 95% CI for each treatment group response rate and the difference in		
	response rate for branebrutinib compared to PBO will be provided. If expected		
	cell counts are not sufficient, then Fisher's exact test will be used. Since this sub-		
	protocol is not powered to determine statistical significance, P-values will be		
Primary	added descriptively.		
	Imputation Method		
	Nonresponder imputation will be used for binary endpoints for subjects who		
	discontinue study treatment early, start a protocol-prohibited medication/therapy		
	prior to the specified timepoint, or otherwise have missing endpoint data for the		
	specified timepoint.		
	Other imputation methods may be considered for sensitivity analyses and will be		
	described in the SAP if used.		
	General Analysis Methodology		
Additional	Response rates of branebrutinib compared to PBO for binary endpoints		
Additional	(responder/nonresponder) will be analyzed using a CMH test stratified by HCQ		
	use. The 95% CI for each treatment group response rate and the difference in		

Protocol Amendment No.: 04

Endpoint	Statistical Analysis Methods
	response rate for branebrutinib compared to PBO will be provided. If expected
	cell counts are not sufficient, then Fisher's exact test will be used.
	Continuous endpoints (change from baseline values) will be analyzed using
	analysis of covariance. The baseline value of the endpoint being tested will be
	added into the model as a covariate and HCQ use and treatment as fixed effects.
	Treatment differences based on least-squares means and corresponding 2-sided 95% CIs will be provided for the difference between branebrutinib and PBO.
	Supportive Analyses
	Supportive Analyses Supportive analyses for continuous endpoints may be performed using MMRM to
	investigate response over time. Bayesian borrowing to utilize historical controls
	may also be performed as supportive analyses. Details will be provided in the SAP
	if needed.
	Imputation Method
	Nonresponder imputation will be used for binary endpoints for subjects who discontinue study treatment early, start a protocol-prohibited medication/therapy
	prior to the specified timepoint, or otherwise have missing endpoint data for the
	specified timepoint.
	Other imputation methods may be considered for sensitivity analyses and will be
	described in the SAP if used.
	Testing Strategy for Additional Endpoints
	There will be no alpha level adjustment for multiple endpoint testing.

pSS 9.4.1.1 Subgroup Analyses

Subgroup analyses will be conducted for the primary and secondary efficacy endpoints on the FAS population. Subgroups that may be evaluated include the following:

- Gender
- Race
- Tobacco use

Additional subgroups defined for descriptive summaries may be specified in the SAP.

pSS 9.4.2 Safety Analyses

Safety data will be descriptive in nature and will be summarized using the Safety Analysis Set. Data will be summarized using descriptive statistics (n, mean, standard deviation, median, minimum, and maximum), unless otherwise specified, for continuous variables and frequency distributions (counts and percentages) for categorical variables. Safety data will be summarized separately for each sub-protocol and with all sub-protocols combined.

Clinical Protocol
BMS-986195
IM014029 - pSS
Branebrutinib

Data will be presented for the following treatments:

- Branebrutinib
- PBO

pSS 9.4.2.1 Adverse Events

TEAEs are defined as AEs that occur after the subject received first dose of study treatment or if a preexisting condition worsens in severity or becomes serious after receiving the first dose of study treatment up to 30 days after the last dose of study treatment. All reported TEAEs, SAEs, deaths, AEs leading to study treatment discontinuation, and target AEIs will be summarized by MedDRA system organ class and preferred term.

pSS 9.4.2.2 Clinical Laboratory Tests

Laboratory parameters will be summarized as absolute and change from baseline values by visit. Baseline values are defined as the last nonmissing value prior to the first dose of study treatment. Marked abnormalities summarized by visit and shift tables will also be provided. For clinical laboratory test results, marked abnormalities will be defined in the SAP.

pSS 9.4.2.3 Vital Signs and ECGs

Vital signs and ECGs will be summarized as absolute and change from baseline values by visit. Baseline values are defined as the last nonmissing value prior to the first dose of study treatment. Marked abnormalities will be summarized by visit as well. For vital signs and ECGs, marked abnormalities will be defined in the SAP.

pSS 9.4.3 Other Analyses

The PK, PD, and exploratory biomarker analyses will be described in the SAP finalized before database lock. Any population pharmacokinetics analysis and PD analyses will be presented separately from the main CSR.

pSS 9.4.4 Analysis and Reporting

After all subjects in the pSS sub-protocol have finished the study and the data have been locked for the sub-protocol, analyses of the efficacy and safety data for the sub-protocol will be performed in order to aid in planning for subsequent clinical development. Details of these analyses will be described in the SAP. The study team responsible for managing the study, including Medical Monitors, will remain blinded to treatment assignment and the results of safety analysis until full database lock and treatment unblinding has occurred. The data will be reported only after completion of all 3 sub-protocols.

Page: 193

Protocol Number: IM014029 IND Number: 142401

EX-US Non-IND

EUDRACT Number: 2019-002205-22

Date: 01-Jul-2019

Revised Date: 01-Dec-2021

Clinical Protocol IM014029:

RA SUB-PROTOCOL

A Randomized, Placebo-Controlled, Double-Blind, Multicenter Study to Assess the Efficacy and Safety of Branebrutinib Treatment in Subjects with Active Systemic Lupus Erythematosus or Primary Sjögren's Syndrome, or Branebrutinib Treatment Followed by Open-label Abatacept Treatment in Subjects with Active Rheumatoid Arthritis

Protocol Amendment 04 RA

11000011	
Study Director	Medical Monitor
Bristol Myers Squibb Company [name]	
Telephone (office):	Medical Monitoring Support Center
Email:	Telephone (office): Mobile:
	Fax:
	Email:
24-hr Emerge USA Internation	
3401	ers Squibb Company [name]

[name]

RA TABLE OF CONTENTS

RA 1	SUB-PROTOCOL SUMMARY	198
RA 1.1	Synopsis	198
RA 1.2	Schema	204
RA 1.3	Schedule of Activities	205
RA 2	INTRODUCTION	220
RA 2.1	Background and Research Hypothesis	220
RA 2.1.1	Study Hypotheses	221
RA 2.2	Benefit/Risk Assessment	221
RA 2.2.1	Branebrutinib	221
RA 2.2.2	Open-label Therapy with Abatacept	222
RA 3	OBJECTIVES AND ENDPOINTS	224
RA 4	STUDY DESIGN	226
RA 4.1	Overall Design	226
RA 4.1.1	DMC and Other External Committees	227
RA 4.2	Number of Subjects	228
RA 4.3	End of Study Definition	228
RA 4.4	Scientific Rationale for Study Design	228
RA 4.5	Justification for Dose	228
RA 5	STUDY POPULATION	230
RA 5.1	Inclusion Criteria	230
RA 5.2	Exclusion Criteria	234

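### pSS 9.1 sizes the sub-protocol on a 95% CI that clears 0 only narrowly and with an unpooled Wald variance; score-type intervals, which match the planned CMH test, just include 0 at the same result

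*Combined protocol and SAP*

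**What the plan says.** Section pSS 9.1 sets out the design: "Assuming a total sample size of 45 subjects randomized in a blinded fashion at a 2:1 ratio to branebrutinib (30 subjects) or PBO (15 subjects"). It assumes "a treatment difference of 30% with a PBO response of 20% for the pSS composite response at Week 24", which puts the branebrutinib rate at 50%. From this it concludes that "the 95% CI is expected to exclude 0 (expected 95% CI based on a z-test = 3%, 57" percent). It states no power and no probability of that outcome.

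Section pSS 9.4.1 (Primary row) plans a different calculation for the analysis. Binary endpoints ("responder/nonresponder) will be analyzed using a CMH test stratified by HCQ" use) are the main comparison, and if expected "cell counts are not sufficient, then Fisher's exact test will be used". A 95% CI for the difference in response rates is also planned, but its method is not named. The same row says that the sub-protocol "protocol is not powered to determine statistical significance, P-values will be" descriptive only. Missing data are handled by counting the subject as a nonresponder, so the denominators stay at 30 and 15.

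**The concern.** The sizing statement uses an unpooled z interval, while the planned test estimates its variance under the hypothesis of no difference. With 45 subjects allocated 2:1 the two forms give noticeably different answers, and the expected result lies between them. A reader of pSS 9.1 would take exclusion of 0 as the likely outcome if the assumptions hold. If it is closer to an even chance, the justification for 45 subjects is weaker than it reads.

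There is a reporting consequence too. If the final interval is also Wald, one table could show a CI that excludes 0 beside a CMH p-value above 0.05. Section pSS 9.4.4 says that these results will inform later development, so the reading of that table matters even without a formal success rule.

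**Working it through.** **Inputs.** n = 30 and 15; rates 50% and 20% (pSS 9.1), hence expected counts 15/30 and 3/15. The test and the fallback come from pSS 9.4.1. The HCQ split and the response rates by HCQ stratum are not given in the text available, so stratified results below rest on illustrative splits.

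**1. The plan's own figure.** Unpooled variance = 0.5×0.5/30 + 0.2×0.8/15 = 0.00833 + 0.01067 = 0.0190; SE = 0.1378. Interval = 0.30 ± 1.96×0.1378 = 2.98% to 57.02%. This reproduces 3%, 57% (z = 2.18, p = 0.030).

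**2. Other intervals at 15/30 versus 3/15.**
- Newcombe: Wilson limits are 0.3315 to 0.6685 (15/30) and 0.0705 to 0.4519 (3/15). Lower limit = 0.30 - sqrt(0.1685² + 0.2519²) = 0.30 - 0.303 = -0.3%. Upper limit = 0.30 + sqrt(0.1685² + 0.1295²) = 51.2%.
- Miettinen-Nurminen: -0.7% to 53.2%.

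Both narrowly include 0.

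**3. Tests at 15/30 versus 3/15.**
- Fisher, two-sided: p = 0.063.
- CMH with one stratum: pooled rate 18/45 = 0.40; chi-square = 0.30² / [0.4×0.6×(1/30 + 1/15)×45/44] = 0.09/0.02455 = 3.667; p = 0.056. The Miettinen-Nurminen interval uses this same variance at a difference of 0, so the two must agree.
- CMH with two proportional strata and response roughly unrelated to HCQ (10/20 v 2/10 and 5/10 v 1/5): p = 0.058.
- CMH with HCQ prognostic (9/15 v 3/8 and 6/15 v 0/7): p = 0.044; (12/20 v 3/10 and 3/10 v 0/5): p = 0.048.
- CMH with an uneven HCQ split (12/22 v 2/8 and 3/8 v 1/7): p = 0.086.

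All of these splits total 15/30 versus 3/15.

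**4. Chance of excluding 0, or of p <= 0.05, in favour of branebrutinib.** Exact enumeration over all outcomes at true rates 50% and 20%:

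| Method | Probability |
|---|---|
| Wald CI | 58% |
| Newcombe CI | 50% |
| One-stratum CMH | 50% |
| Fisher | 42% |

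**5. Error and disagreement.** With both arms at 20%, the Wald lower limit exceeds 0 in 5.0% of trials, against a nominal 2.5%. At 50% versus 20%, the Wald interval excludes 0 while one-stratum CMH p > 0.05 in 8.7% of trials.

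**The case against.** The strongest reply is that pSS 9.1 makes a precision statement, names its method, gets the number right, and is explicitly conditional on the assumed rates. It promises no power. RA 9.1 does state power (82%), so the sponsor gives power where it intends to. pSS 9.4.1 disclaims power and makes p-values descriptive, and no decision rule turns on 0.05. The SAP is still to be finalised and could name any interval method. All of this stands, and it limits the weight of the point.

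Several stronger readings are tempting, and the documents do not support them:
- A reader might infer a calculation error. There is none: the interval reproduces.
- A reader might infer that only an unstratified interval excludes 0. A Mantel-Haenszel stratified Wald interval on the proportional split above also gives 3.0% to 57.0%, and the profile-likelihood lower limit is +0.5%. What matters is the variance form, not the absence of stratification.
- A reader might infer that the planned CMH test necessarily misses 0.05 at this result. It depends on by-stratum counts that are not given, and it falls below 0.05 in some prognostic splits.
- A reader might infer that Fisher's test is bound to replace the stratified test. The plan sets no threshold. The smallest expected count in the overall table is 15×18/45 = 6. Counts per stratum would be smaller, but nothing says that the rule applies per stratum.

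What the reply does not remove is that pSS 9.1 makes its claim about the interval itself. Calling p-values descriptive does not make exclusion of 0 more probable.

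**Conclusion.** The point holds as a mismatch between the sizing statement and the planned analysis. At exactly the assumed result, the Wald interval clears 0 by 3 percentage points, while the two score-type intervals miss by less than 1. If the assumed rates are true, exclusion of 0 is roughly an even chance: 42% to 58% by method, and about 50% for the methods closest to the planned test. The Wald interval is also anti-conservative here, with a lower-tail error of 5.0% against 2.5% when both arms respond at 20%.

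These figures assume 30 and 15 analysed subjects, and rates of 50% and 20% after nonresponder imputation. The CMH range of about 0.056 to 0.058 further assumes proportional HCQ strata and little HCQ effect on response. Whether the final analysis will use a Wald interval is not established, because the method is unnamed. The pSS synopsis and a separate SAP were not available, so further sizing rationale may exist there. The matter should be corrected, but it does not undermine a descriptive Phase 2a comparison.

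**What to change.** 1. Restate pSS 9.1 along these lines: *if 50% versus 20% is observed, the 95% score CI is about -1% to 53%; the probability that the 95% CI excludes 0 is about 50%.*
2. In pSS 9.4.1 and the SAP, name the interval for the difference as Miettinen-Nurminen (score), stratified by HCQ use. With Mantel-Haenszel weights and no continuity correction, its variance at a difference of 0 is that of the CMH statistic, so the interval and the p-value will agree.
3. Optional: say when expected counts are insufficient, and keep the HCQ stratification in whatever small-count test is used.

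The cost is protocol and SAP wording, and a stated expectation that is less favourable than the present one. No patients are added.
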